#### **2.4 Ipilimumab (anti-CTLA-4 antibody)**

Ipilimumab is a monoclonal antibody that blocks the immunosuppressive receptor CTLA-4 on T cells, thus enhancing (disinhibiting) immune responses against the tumor. Because of the role CTLA-4 plays in undermining antitumor T cell responses, the use of CTLA-4 blockade in combination with a range of cancer immunotherapies has been investigated in preclinical models and found to enhance antitumor T cell responsiveness. Ipilimumab has recently been approved by the FDA for unresectable and metastatic melanoma, and has demonstrated preliminary anti-tumor effect as a single agent in other solid tumors, including metastatic NSCLC and prostate carcinoma.

Treatment with ipilimumab increases median overall survival in both previously untreated and previously treated patients with metastatic Stage III or IV melanoma (Hodi *et al.*, 2010; Robert *et al.*, 2011). Increase in median survival was approximately 2 to 4 months, but >90% of patients eventually progressed. Ipilimumab (Yervoy®) is currently approved for metastatic or unresectable melanoma at a dose of 3 mg/ kg every 3 weeks.

## **2.5 PD-1 Checkpoint Inhibitors (Nivolumab and Pembrolizumab)**

Two anti-programmed death 1 (PD-1) antibodies, nivolumab and pembrolizumab, were approved in 2014 by the Food and Drug Administration for the treatment of metastatic melanoma after progression during ipilimumab treatment and, in patients with BRAF-mutated melanoma, after progression during treatment with a BRAF inhibitor. These antibodies were associated with objective responses in 30 to 40% of patients. Two phase 3 trials have shown superior efficacy of nivolumab, as compared with chemotherapy, in previously untreated patients with wild-type BRAF tumors or in patients with either mutant or wild-type BRAF tumors after progression during ipilimumab therapy and, in patients with tumors positive for BRAF mutation, after progression during treatment with a BRAF inhibitor (Robert C, NEJM, 2015 and Weber JS, Lancet, 2015). Recently, pembrolizumab was associated with longer progression-free survival and overall survival and higher response rates than those associated with ipilimumab in a phase 3 trial involving patients with advanced melanoma (Robert C, NEJM, 2015).

In May 2015, results from the CheckMate 067 trial were presented. This study involving patients with previously untreated advanced melanoma, treatment with nivolumab alone or with the combination of nivolumab and ipilimumab resulted in significantly longer progression-free survival and higher objective response rates than did treatment with ipilimumab alone. The incidence of adverse events in this study was, in general, lowest in the nivolumab group and highest in the combination group.

Pembrolizumab was first evaluated in the large, phase 1 KEYNOTE-001 study (Robert C, Lancet, 2014). In a pooled analysis of 411 patients with advanced melanoma enrolled in KEYNOTE-001 and after a median follow-up duration of 18 months, the response rate was 34%, the response was maintained in 81% of those patients, and median overall survival was 25.9 months (Ribas A, 2014)

In KEYNOTE-006 PD-1 inhibition is compared with CTLA-4 blockade in a controlled, randomized trial involving patients with advanced melanoma. The estimated 6-month progression-free survival rates were 47.3% for patients receiving pembrolizumab every 2 weeks, 46.4% for those receiving pembrolizumab every 3 weeks, and 26.5% for those receiving ipilimumab. Median estimates of progression-free survival were 5.5 months (95% confidence interval [CI], 3.4 to 6.9), 4.1 months (95% CI, 2.9 to 6.9), and 2.8 months (95% CI, 2.8 to 2.9), respectively. One-year estimates of survival were 74.1% for patients receiving pembrolizumab every 2 weeks (hazard ratio for death as compared with the ipilimumab group, 0.63; 95% CI, 0.47 to 0.83;  $P < 0.0005$ ), 68.4% for those receiving pembrolizumab every 3 weeks (hazard ratio for death as compared with the ipilimumab group, 0.69; 95% CI, 0.52 to 0.90;  $P = 0.0036$ ), and 58.2% for those receiving ipilimumab (Roberts C, NEJM, 2015).

Based on these data, many clinician are changing practice patterns to use PD-1 inhibitors (nivolumab and pembrolizumab) as first line treatment in preference to ipilimumab.

## 2.6 Rationale for Combining Checkpoint Inhibitors with Dorgenmeltucel-L

Preclinical data have demonstrated synergy between vaccine approaches to cancer treatment and checkpoint inhibitors. In a murine model of melanoma, the combination of a whole cell vaccine and ipilimumab showed synergistic results (Holmgaard, NEJM, 2015). The goal of this study is to apply this approach to patients with metastatic melanoma, combining a HyperAcute immunotherapy whole cell vaccine with the immune checkpoints ipilimumab, nivolumab, or pembrolizumab.

## 3 PATIENT SELECTION

### 3.1 Eligibility criteria

Must be confirmed within 30 days prior to study enrollment/registration, except for  $\beta$ -HCG (confirm within 1 week) when appropriate. Subjects who are positive (+) for the BRAF mutation who have not received BRAF inhibitors yet, may be enrolled to this study based on the discretion of the treating physician and may receive BRAF inhibitors following this study.

#### Inclusion criteria:

- Histological/cytological diagnosis of melanoma.
- AJCC Stage IV (any T, any N, M1), metastatic, progressive, refractory, melanoma.
- Patients may have advanced unresectable Stage IV disease, resectable Stage IV disease, or recently resected Stage IV disease (<10 weeks prior) with no apparent disease (NAD)
- Eastern Cooperative Oncology Group (ECOG) Performance Status  $\leq 1$  (see **Appendix B**).
- Serum albumin  $\geq 3.0$  gm/dL.
- Adequate organ function including:
  - Marrow: Hemoglobin  $\geq 10.0$  gm/dL, absolute granulocyte count (AGC)  $\geq 1,000/\text{mm}^3$ , platelets  $\geq 75,000/\text{mm}^3$ , absolute lymphocyte count  $\geq 475/\text{mm}^3$ .
  - Hepatic: Serum total bilirubin  $\leq 2.5$  x upper limit of normal (ULN), ALT (SGPT) and AST (SGOT)  $\leq 2.5$  x ULN.
  - Renal: Serum creatinine (sCr)  $\leq 1.5$  x ULN.
- Prior therapy for melanoma that may include surgery, radiation therapy, immunotherapy including interleukins and interferon, and/or  $\leq 2$  different regimens of systemic chemotherapy, targeted therapy, or other experimental systemic therapies. Prior treatment with immune checkpoint inhibitors is not allowed (see Exclusion criteria).
- Patients must be  $\geq 4$  weeks since major surgery, radiotherapy, chemotherapy (6 weeks if they were treated with nitrosureas) or biotherapy/targeted therapies.
- Patients must have the ability to understand the study, its risks, side effects, potential benefits and be able to give written informed consent to participate. Patients may not be consented by a durable power of attorney (DPA).
- Male and female subjects of child producing potential must agree to use *contraception or avoidance of pregnancy measures* while enrolled on study and receiving the experimental drug, and for one month after the last immunization.

Exclusion criteria:

- Age <18-years-old.
- *Active* CNS metastases or carcinomatous meningitis. Patients with CNS lesions that have been treated and who have no evidence of progression in the brain on CT/MRI for  $\geq 1$  month are eligible.
- Pregnant or nursing women due to the unknown effects of immunization on the developing fetus or newborn infant.
- Other malignancy within five years, except that the following may be eligible:
  - patients curatively treated for localized squamous or basal cell carcinoma of the skin or for carcinoma *in situ* of the uterine cervix (CIN) or breast,
  - patients with a history of malignant tumor who have been disease free for at least five years and are not currently being treated.
- History of an allogeneic solid organ transplant or bone marrow transplant, or current active immunosuppressive therapy such as cyclosporine, tacrolimus, etc.
- Subjects taking systemic (parentally or orally) corticosteroid therapy for any reason, including replacement therapy for hypoadrenalism, are not eligible. Topical steroids are acceptable as are intranasal steroids.
- Active infection or antibiotics within 48 hours prior to study enrollment, including unexplained fever (temp  $> 38.1^{\circ}\text{C}$ ), if deemed clinically significant by the treating physician.
- Evidence of *active* autoimmune disease (e.g., systemic lupus erythematosus, rheumatoid arthritis, with the exception of vitiligo. Patients with a remote history of asthma or mild asthma are eligible.
- Other serious medical conditions that may be expected to limit life expectancy to less than 2 years (e.g., liver cirrhosis).
- Any condition, psychiatric or otherwise, that would preclude informed consent, consistent follow-up or compliance with any aspect of the study (e.g., untreated schizophrenia or other significant cognitive impairment, etc.).
- Patients having previously undergone splenectomy.
- Patients with known hepatitis or unstable liver disease, and/or positive serologies for Hepatitis B or C and HIV.
- Patients with sickle-cell anemia or thalassemia major.
- Subjects who received prior treatment with immune checkpoint inhibition consisting of ipilimumab, tremelimumab, nivolumab, pembrolizumab or other antibody to CTLA4 or PD-1.

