## **6 DOSING DELAYS/DOSE MODIFICATIONS**

The dosing delay and modification information contained in this section concerning ipilimumab, nivolumab, and pembrolizumab is provided for background purposes. Dosing delays and / or modification of these agents should be performed consistent with standard of care practice by the treating physician within the guidelines provided in the respective package inserts.

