### **6.3 Ipilimumab Dose Modifications**

The administration of ipilimumab under this protocol is to be within accordance with the package insert for ipilimumab. This includes toxicity management and dosing adjustments or discontinuation of ipilimumab. The following is intended to highlight aspects of management.

- Ipilimumab related toxicities must be resolved to baseline or  $\leq$  Grade 1 prior to administering the next dose.
- No dose reductions for ipilimumab are allowed.
- Ipilimumab can be delayed if the reason for the delay is toxicity/AE and if resolved to Grade 1 or better can restart and continue every 3 weeks until all 4 planned doses are administered or 16 weeks from first dose, whichever occurs earlier.
- Please refer to the AE management algorithms provided by the package insert for ipilimumab on management of potentially ipilimumab-related adverse events (also in **Appendix D**).
- Liver function tests (AST, ALT total bilirubin) will be evaluated for every subject prior to administration of ipilimumab. Blood samples must be collected and analyzed within 3 days prior to dosing. Liver function test results must be reviewed by the principal investigator or designee prior to ipilimumab administration and meet dosing criteria specifications:
  - $< 2.5 \times$  ULN for AST and ALT and  $< 1.5 \times$  ULN for total bilirubin
- If abnormal LFT values are detected, the subject must be managed using hepatotoxicity algorithm (see **Appendix D**).

Treatment may resume when the AE(s) resolve(s) to Grade 1 or baseline value.

During ipilimumab administration, ipilimumab must be permanently discontinued if the subject experiences any of the following toxicities. Events requiring permanent discontinuation are:

- Grade 3 or 4 motor or sensory neuropathy, regardless of causality
- Any AE which, in the judgment of the investigator, presents a substantial clinical risk to the subject with investigational drug dosing.
- Any  $\geq$  Grade 2 eye pain or reduction of visual acuity that does not respond to topical therapy and does not improve to Grade 1 or better severity with topical therapy or requires systemic treatment.
- Any other  $\geq$  Grade 3 non-skin related AE with the exception of laboratory abnormalities and Grade 3 nausea and vomiting.
- Any Grade 4 laboratory abnormalities
- Persistent Grade 2 adverse reactions (that push ipilimumab administration beyond the

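### The entry limit for total bilirubin (≤ 2.5 × ULN) is looser than the ipilimumab pre-dose criterion (< 1.5 × ULN), so a patient declared for ipilimumab can be randomised without qualifying for the first dose

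*Combined protocol and SAP*

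**What the plan says.** **Entry.** In the Section 3.1 inclusion criteria, the item "Hepatic: Serum total bilirubin" sets a ceiling of 2.5 × ULN, inclusive. It is one limit for all patients and does not vary with the checkpoint inhibitor. Section 4.1 has the physician name that agent before the patient is enrolled.

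**Dosing.** Section 6.3 applies a liver check to every subject before ipilimumab. On timing: "Blood samples must be collected and analyzed within 3 days prior to dosing". On force: "Liver function test results must be reviewed by the principal investigator or designee prior to ipilimumab administration and meet dosing criteria specifications". The listed bilirubin criterion is < 1.5 × ULN. For values outside the limits: "If abnormal LFT values are detected, the subject must be managed using hepatotoxicity algorithm", with a pointer to Appendix D.

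**References to baseline in Section 6.3.** There are two. One begins "Ipilimumab related toxicities must be resolved to baseline or" and goes on to Grade 1 or better, as a condition for the next dose. The other reads "Treatment may resume when the AE(s) resolve(s) to Grade 1 or baseline value".

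**Status of this text.** Section 6 opens by saying that its dosing-delay and modification information "concerning ipilimumab, nivolumab, and pembrolizumab is provided for background purposes", and it defers to standard of care within the package inserts. Section 5 likewise leaves administration to the treating physician. Section 6.3 introduces its own list with "The following is intended to highlight aspects of management".

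**The concern.** Two stated rules disagree about the same laboratory value. The registration rule lets a patient in, and the dosing rule, read plainly, then withholds the drug named at registration. Because the agent is declared before enrolment, the disagreement could be settled at that point. As written, it surfaces only after randomisation.

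What is at stake is delivery of the assigned treatment, and the two ipilimumab arms meet the problem differently. In Arm 2A ipilimumab is the whole of study treatment and is due on Day 1, while Section 4.2 requires treatment to start within 4 weeks of registration. In Arm 1A the patient can start the vaccine on time and meets the ipilimumab criterion only at Day 22. Such a patient stays in the full analysis set in either arm. That is ordinary intention-to-treat handling, but the assigned ipilimumab may be late or absent.

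**Working it through.** The plan states no figure to reproduce. The check compares thresholds, and no sample-size or power calculation enters.

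**Inputs**

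| Item | Value | Source |
|---|---|---|
| Entry limit, total bilirubin, all agents | ≤ 2.5 × ULN | Section 3.1 |
| Ipilimumab pre-dose limit, total bilirubin | < 1.5 × ULN | Section 6.3 |
| Sampling window for the pre-dose check | within 3 days | Section 6.3 |
| First ipilimumab dose, Arm 2A | Day 1 | Protocol schema, Arms 1A and 2A |
| First ipilimumab dose, Arm 1A | Day 22 | same schema |
| Vaccine doses before that in Arm 1A | Days 1, 8, 15 | same schema |
| Latest start of treatment | 4 weeks from registration | Section 4.2 |

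**Step 1: the band where the rules disagree.** Let b be total bilirubin as a multiple of ULN. Entry requires b ≤ 2.5 and ipilimumab dosing requires b < 1.5. A patient passes the first and fails the second when 1.5 ≤ b ≤ 2.5, a band of 2.5 − 1.5 = 1.0 × ULN. For AST and ALT the limits are ≤ 2.5 at entry and < 2.5 before dosing, so they differ only at exactly 2.5 × ULN. That can be left alone.

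**Step 2: whether the first dose is exempt.** It is not. The check covers every subject before ipilimumab is given. A patient in the band therefore fails it and is referred to Appendix D.

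**Step 3: whether the baseline wording resolves the case.** The first reference concerns toxicity related to ipilimumab before a further dose. The second concerns resuming after an adverse event. A patient who has had no ipilimumab has neither. The wording also fits poorly when the baseline value is itself at or above 1.5 × ULN. The available text of the protocol contains no rule written for bilirubin already raised at entry, such as a waiver, a change of agent or removal from study. Appendix D might contain one.

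**Step 4: consequence by arm.** In Arm 2A the failed check falls on Day 1 and the 4-week start limit is running. In Arm 1A the vaccine starts treatment and the check falls on Day 22, after 3 vaccine doses.

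**Step 5: how many patients.** Write p for the share of patients declared for ipilimumab and q for the share of those in the band. The expected number among the 100 planned patients is 100 × p × q. The documents give neither p nor q, so the number cannot be computed. Three features point to a small group:

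- Physicians see baseline bilirubin before they declare an agent.
- Section 2.5 notes a move to PD-1 inhibitors in first line.
- Section 3.1 excludes known hepatitis and unstable liver disease.

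None of these stops a physician from declaring ipilimumab for an otherwise eligible patient in the band.

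**The case against.** The best case for leaving the plan alone has four parts.

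- **The first dose is covered.** Section 6.3 holds it and names an algorithm. This stands. A reader might infer that the plan leaves the first dose with no rule at all, and the documents do not support that. Appendix D is cited, and its content cannot be called missing merely because it was not available here.
- **The text is labelled background.** Sections 5 and 6 defer to the physician and the package inserts. This stands as a reason for low severity, because how strictly the limit binds is open. It does not remove the mismatch. Section 6.3 uses mandatory wording for the sampling, for meeting the criteria and for managing abnormal values, so one site could treat the limit as binding and another as advisory.
- **An entry limit may properly be looser than a per-dose limit.** One organ-function limit serves three agents and a vaccine, bilirubin can change between screening and dosing, and a held dose is the safety check doing its work. This is fair as a general principle. It is weaker here because the agent is known at registration and, in Arm 2A, nothing else is given.
- **Randomisation spreads affected patients over both arms.** Checkpoint inhibitor choice is a stratification factor in Section 12.2, so no systematic excess in one arm is expected. This stands, and no imbalance is alleged. The difference lies in when the check falls and what else the patient is receiving.

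A reader might also infer the same conflict for nivolumab and pembrolizumab, since Sections 6.4 and 6.5 withhold those drugs at bilirubin above 1.5 and up to 3 × ULN. The numerical overlap with the entry range is real. However, those are withholding rules, with resumption after an adverse reaction recovers, and not a stated pre-dose criterion like the one in Section 6.3. The point is therefore confined to ipilimumab.

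**Conclusion.** The point holds as a minor, low-severity inconsistency. For total bilirubin from 1.5 to 2.5 × ULN, Section 3.1 admits a patient declared for ipilimumab whom Section 6.3, read plainly, would not dose. Section 6.3 sends that patient to Appendix D, and no available text addresses a value already raised at entry. The effect is a delayed or missing assigned treatment from Day 1 in Arm 2A, and a question that first arises at Day 22 in Arm 1A.

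This rests on two assumptions: that sites apply the Section 6.3 criterion as written despite the background label, and that Appendix D has no rule for raised baseline bilirubin. If either fails, the point shrinks to a missing cross-reference or a clarification of wording.

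A reader might infer a loss of power or a safety hazard. The documents support neither. The number affected is probably small and cannot be computed, and the dosing check itself is protective.

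**What to change.** Add to the hepatic criterion in Section 3.1, and to the Eligibility Checklist Form: *For patients whose declared checkpoint inhibitor is ipilimumab, total bilirubin at screening must be < 1.5 × ULN.* If Appendix D already sets a rule for bilirubin raised at baseline, cite that rule in Section 3.1 instead. Leave the AST/ALT limits and the limits for the other two agents as they are.

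The cost is one sentence and one checklist line. A few candidates become ineligible for ipilimumab, including some whose bilirubin would have fallen below the limit by the first dose. The sentence also makes a limit from text labelled background binding at entry, so the sponsor should confirm that this is intended. Bilirubin can rise after screening, so failed first-dose checks become fewer but do not disappear. Declaring a PD-1 agent for these candidates should not be offered as a clean alternative until the withholding ranges in Sections 6.4 and 6.5 have been checked against their bilirubin values.

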### 3.2 *Eligibility and On-Study Tests*

Baseline and on-study tests will include (see Section 8.0 Study Calendar):

- Baseline history and complete physical examination
- Serum chemistries including electrolytes, BUN, creatinine, calcium, glucose and albumin; liver function tests including total bilirubin, ALT (SGPT) AST (SGOT), LDH, and alkaline phosphatase; quantitative immunoglobulins (IgG, IgM, and IgE); CBC with platelets and differential.

- Thyroid stimulating hormone (TSH) and free T4.
- Pregnancy testing with serum  $\beta$ -HCG in women of child-bearing potential
- Blood (approximately 16 mL) for measurement of anti-*agal* and anti-tumor antibodies to be drawn on Day 1 before treatment administration and as outlined in Section 8.
- For patients receiving the dorgenmeltucel-L immunotherapy, whole blood (approximately 10 mL) for replication competent retrovirus (RCR) testing on Day 1 prior to the first immunization and will be sent to NewLink Genetics.
- Contrast enhanced CT-scan of the chest and abdomen *or* whole body PET/CT fusion scan. CT-scan or MRI scan of the brain if known or suspected brain metastases. If indicated, CT scan of the neck, *or* ultrasound, PET-scan and/or radionuclide bone scan may also be obtained. PET scans and radionuclide bone scans may not be used for determination of response.
- Measurable disease or solid lesions, liver masses, lymph nodes and skin nodules will be measured and recorded pre-therapy using RECIST/irRC criteria.
- Whole blood (approximately 100 mL) in purple top tubes for PBLs for intracellular cytokines and ELISPOT to be drawn on Day 1 before treatment administration and as outlined in Section 8. These samples will be sent to NewLink Genetics for testing.

Baseline evaluations are to be conducted within 30 days prior to start of protocol therapy unless otherwise specified. In the event that the patient's condition has significantly deteriorated (e.g., significant increase in symptoms or worsening of ECOG PS), laboratory evaluations should be repeated within 5 days prior to initiation of therapy.

## 4 TREATMENT PLAN

### 4.1 *Registration and Randomization*

All patients must be registered on study before beginning therapy. Treating physician must declare which immune checkpoint therapy will be used prior to enrolling a patient.

All subjects must have: (1) a signed Informed Consent Document and, (2) a completed Eligibility Checklist Form before registration on the study. To register a subject for this protocol, an authorized physician or their designee must FAX or EMAIL the subject information to the NewLink Genetics Registration Office or the site's designated CRA between the hours of 8:30 A.M. and 5:00 P.M. Central Standard Time, Monday through Friday. (FAX: [REDACTED] EMAIL: [REDACTED]). No evening, weekend or holiday registrations will be permitted. An online randomization process will be used to provide sites with treatment assignments for this study. A randomization plan will be provided to the sites detailing the process. Once eligibility and disease status stratum is confirmed by NewLink and the subject randomized, NewLink will FAX or EMAIL a confirmation of registration to the site. The treatment assignment will be provided to the site by EMAIL. The clinical site's storage facility/pharmacy will not release the immunotherapy until the day of the scheduled immunization.

A file of copies of all reports, laboratory studies and other pertinent information documenting the subject's eligibility for study will be maintained in the Clinical Research Office of NewLink Genetics Corporation.

